### Primary Objectives and Sample Size:

The first primary objective is to evaluate whether pulsatile lapatinib, when given on the pulsatile dosing schedule, can reach an intratumoral concentration of 1.5  $\mu\text{M}$  or higher in 70% of patients with recurrent and surgically accessible EGFR-amplified high-grade glioma.

Initially eight patients will be treated with pulsatile lapatinib and the intratumoral concentration of lapatinib will be analyzed.

- if no more than 2 patients achieve adequate tumor lapatinib concentration of 1.5  $\mu\text{M}$  or higher, the trial will be stopped early for futility. The probability of early stopping for futility is 68% with a true null of 25% while maintaining only 1.1% probability of early termination for a true rate of 70% (the target).
- if 3 or more of the initial 8 patients reach an intratumoral drug concentration level of 1.5  $\mu\text{M}$  or higher, 10 additional patients will be enrolled into the study.
- if 8 or more of the 18 patients treated with pulsatile lapatinib achieve intratumoral lapatinib concentrations of at least 1.5  $\mu\text{M}$ , the PK objective will be met. This

design has 98% power to detect a true rate of 70% from a null of 25% in achieving lapatinib intratumoral concentration level of 1.5  $\mu$ M with a false positive rate of 0.05.

The PD study will be pursued after the initial 8 patients' PK objective is met.

The primary PD objective is to test the hypothesis that 70% of patients will achieve 80% reduction in ratio of phosphorylated to total EGFR after pulsatile lapatinib treatment assuming a null of 25% patients. A ratio of pEGFR/total EGFR at 80% reduction from a median value from the untreated reference group will be considered as the putative threshold to qualify a near complete inhibition of EGFR (at 80%). If at least 9 (50%) of the 18 treated patients demonstrate a pEGFR/total EGFR ratio which corresponds to at least an 80% reduction compared to the median pEGFR/total EGFR ratio for the 15 patients enrolled on the reference arm, the PD objective will be met. This design yields 98% power to detect a true 70% rate of near complete (80%) EGFR inhibition and it yields a false positive rate of 2% for a true 25% rate of such EGFR inhibition.

Initial safety monitoring: All adverse events will be monitored and collected throughout the trial and documented based on CTCAE version 5.0. If there are three or more delays of scheduled surgery due to lapatinib-related Serious Adverse Events among the initial 8 patients; or if there are any surgical complications and delayed wound healing SAEs grade  $\geq 3$  considered lapatinib-related among the first three patients, ABTC investigators will consult with CTEP investigators and the pharmaceutical sponsor about such events. An internal safety monitoring evaluation will be conducted after the first three patients complete their first follow-up visit after surgery.

Reference Group (for primary PD study):

15 lapatinib-naïve patients with recurrent and surgically accessible EGFR-amplified high-grade glioma will be enrolled as a reference group for the PD evaluation to establish the threshold of 80% reduction in the ratio of pEGFR/total EGFR. After the initial 8 patients are enrolled into Group A, eligible patients will be sequentially assigned to either treatment group or reference group. The sample size of 15 patients on the reference arm yields 90% confidence that the observed median falls between the true 30th and 70th percentiles of the pEGFR/total EGFR distribution for untreated patients.

To avoid batch effect and other variations through tumor sample processing, all tumor samples will be processed at the same time at the [name] Lab, Memorial Sloan-Kettering Cancer Center.

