Unfortunately, current dosing schedules of lapatinib do not reach sufficiently high intratumoral drug concentrations to potently inhibit EGFR in GBM. When given at a dose of 750 mg twice daily (NABTC 04-01 in Vivanco et al. 2012), lapatinib only inhibited EGFR by about 50 % (based on ratio of phosphorylated to total EGFR using the MSD mesoscale assay [Vivanco et al. 2012]) and failed to prolong progression-free survival in patients with recurrent GBM in that study, and another recent phase I/II trial (Thiessen et al. 2010). Unfortunately, these trials did not restrict patient enrollment to EGFR-mutant GBMs. In the NABTC 04-01 study, for example, neither of the two GBM patients with intratumoral lapatinib concentrations shown to induce cell death in-vitro (>1,500 nM) and EGFR protein overexpression could be evaluated for therapeutic response.

The current trial restricts enrollment to patients with EGFR amplified high grade glioma because glioma cells with amplification of wildtype EGFR gene are more sensitive to lapatinib than cells with non-amplified wildtype EGFR (Vivanco et al. 2012). Furthermore,

the EGFR VIII mutation in GBM occurs almost exclusively in the setting of EGFR gene amplification and EGFRvIII showed greater sensitivity to type II EGFR kinase inhibitors (such as lapatinib) than to the type I EGFR kinase inhibitor erlotinib.

The pharmacokinetic (PK) goal of this study is to achieve intratumoral concentrations of lapatinib >1,500 nM. The pharmacodynamic (PD) goal is to achieve near complete inhibition of pEGFR, defined as 80% reduction of EGFR phosphorylation. Of note, the feasibility of such “pulsatile” lapatinib therapy has already been explored in advanced solid tumors and found to be well tolerated (Chien et al. 2009).

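### The PD rule's 98% power and 2% false positive rate assume a known threshold, and are attached to patients' own EGFR inhibition, which the rule does not observe

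*Combined protocol and SAP*

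**What the plan says.** Section 11.0 (Primary Objectives and Sample Size) words the PD aim at patient level, namely "test the hypothesis that 70% of patients will achieve 80% reduction in ratio of phosphorylated to total EGFR after pulsatile lapatinib treatment". The null rate is set at 25%. The opening paragraph of Section 11.0 has the same patient-level wording.

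The classification is made differently. "A ratio of pEGFR/total EGFR at 80% reduction from a median value from the untreated reference group" serves as the threshold, which the plan itself calls putative. The objective is met as follows: "If at least 9 (50%) of the 18 treated patients demonstrate a pEGFR/total EGFR ratio" at or below that threshold. The operating characteristics come next: "This design yields 98% power to detect a true 70% rate of near complete (80%) EGFR inhibition". The plan puts the chance of a false positive result at 2% when the real rate is 25%.

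Two further places matter:
- Table 9.5 takes frozen tissue for EGFR phosphorylation at protocol surgery only. The archived material is paraffin, used for FISH and immunohistochemistry. Group A therefore has no pre-dose pEGFR value.
- The Reference Group paragraph of Section 11.0 says that 15 patients place the observed median between the true 30th and 70th percentiles with 90% confidence. The PD power and false positive rate make no use of this.

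**The concern.** A patient's own reduction and a tumour's position relative to other patients' median are different quantities. A treated tumour can fall below the cut because the drug worked or because its untreated ratio was already low. It can miss the cut because its untreated ratio was high. The cut is also an estimate from 15 tumours. It is shared by all 18 classifications, so an error in it moves all of them in the same direction.

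The 98% and 2% allow for neither source of variation. This is one of two primary objectives, and Section 4.0 uses it to judge whether the regimen gives enough EGFR inhibition for later studies. If the real false positive rate is several times 2%, a met PD objective is weaker evidence than the plan suggests.

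**Working it through.** **Inputs from Section 11.0.** 18 treated patients, success at 9 or more, null rate 0.25, target rate 0.70, threshold at 20% of the median of 15 reference patients. The between-patient spread is not given, so it is varied below.

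**Step 1: the plan's own figures.** With X ~ Bin(18, p):
- P(X ≥ 9 | p = 0.70) = 0.979, stated as 98%.
- P(X ≥ 9 | p = 0.25) = 0.0193, stated as 2%.
- The 90% statement about the median also reproduces. The 8th of 15 order statistics follows Beta(8, 8) on the percentile scale, and P(0.30 to 0.70) = 0.89997.

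The arithmetic is right for a fixed threshold with p as the share of treated tumours below it.

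**Step 2: same meaning of the rate, median estimated.** Take log ratios as normal, with SD σ_R in the reference group and σ_T in the treated group. Let z_p be the normal quantile of the true share p, and m the sample median of 15 standard normal draws. Given m, each treated tumour is classified as inhibited with probability Φ(z_p + (σ_R/σ_T)·m). Averaging P(X ≥ 9) over 400,000 simulated medians gives:

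| σ_R/σ_T | Power at 70% | False positive rate at 25% |
|---|---|---|
| 0.5 | 96% | 3.5% |
| 1 | 91.5% | 8.1% |
| 2 | 80% | 19% |

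With equal spread, the result does not depend on how large the spread is.

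**Step 3: the rate read as patients' own inhibition.** Let the log untreated ratio have SD σ and the log residual fraction (treated over own untreated) have SD τ, independent of each other. With a known threshold the classified rate is Φ(z_p·τ/√(σ² + τ²)), where z_0.70 = 0.524 and z_0.25 = −0.674. The multiplier on z_p is 0.447, 0.707 and 0.894 at τ/σ = 0.5, 1 and 2.

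| τ/σ | True 70% reads as | True 25% reads as | Known threshold: power / false positive | Median estimated from 15: power / false positive |
|---|---|---|---|---|
| 0.5 | 59% | 38% | 85% / 21% | 77% / 28% |
| 1 | 64% | 32% | 93% / 8% | 88% / 13% |
| 2 | 68% | 27% | 97% / 3% | 95% / 5% |

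The last column combines both effects. The column before it isolates the use of other patients as the comparator. With no spread in untreated ratios (σ = 0), 98% and 2% return.

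**Step 4: correlation.** If the log untreated ratio and log residual fraction have correlation ρ, the denominator becomes √(σ² + τ² + 2ρστ). With a known threshold:
- τ/σ = 1, ρ = −0.5: 1 + 1 − 1 = 1, so the multiplier is 1/1 and 98%/2% return exactly.
- τ/σ = 2, ρ = −0.25: 1 + 4 − 1 = 4, so the multiplier is 2/2 and 98%/2% return again.
- τ/σ = 2, ρ = −0.5: 1 + 4 − 2 = 3, so the multiplier is 2/√3 = 1.155, giving 99% and 0.8%, better than stated.
- Positive ρ makes the figures worse.

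**Step 5: uniform inhibition.**
- Exactly 80% in every patient: a tumour falls below the cut only if its own untreated ratio was below the median, so p = 0.5 whatever the spread. With a known threshold, P(X ≥ 9) = 59%, although every patient meets the criterion.
- Exactly 75% in every patient, so nobody meets it: with the median estimated, the rule passes 2.9% of the time at untreated log-SD 0.25 and 19% at 0.5.
- Exactly 90% in every patient: with the median estimated, it passes 99.96% of the time at log-SD 0.5 and 96% at 1.0.

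**The case against.** The rule is openly defined. Primary Objective 2 in Section 1.0 compares Group A tumours with Reference Group tumours, Section 4.0 says inhibition is judged by that comparison, and Section 11.0 calls the cut putative. The rate in the power statement can fairly be read as the classification just described. One frozen sample per patient rules out an own-baseline measure in any case. The plan also limits spread: EGFR-amplified tumours only, normalisation to total EGFR, tumour content above 80%, freezing within 5 minutes and a single assay batch.

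Much of this stands. Nothing is hidden and the binomial arithmetic is correct. On the charitable reading the comparator problem becomes one of labelling. That reading does not rescue 98% and 2%, because the threshold is still estimated (Step 2). The handling controls may reduce spread, but with equal spread in the two groups Step 2 is the same at any size of spread.

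A reader might infer two stronger things that the documents do not support:
- That a drug which inhibits fully is likely to fail. The 59% belongs to the 80% boundary. At uniform 90% inhibition, failure is at most about 4% for log-SD up to 1.0.
- That the classified rate is always pulled towards 50%. This needs inhibition to be independent of the untreated ratio, or at least not strongly negatively correlated with it. The documents give neither the spreads nor the correlation.

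**Conclusion.** The PD operating characteristics are wrong as written and should be corrected. They are not a miscalculation. They are fixed-threshold binomial figures attached to a rate the rule does not observe.

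The firmer part is the estimated median. With equal log-normal spread, power is about 91.5% and the false positive rate about 8%. These range from 96%/3.5% to 80%/19% as the reference-to-treated spread ratio goes from 0.5 to 2.

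The conditional part is own-patient inhibition. With a known threshold, power is 85/93/97% and the false positive rate 21/8/3% at τ/σ = 0.5/1/2. With the median estimated, they are 77/88/95% and 28/13/5%. This assumes log-normality and independence, neither of which the documents establish.

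Not modelled: the PK futility look after 8 patients, assay error, and the first 8 Group A patients being enrolled before the reference group. A reader might infer that the PD design is unusable. The documents do not support that, since the rule is explicit and can be kept with an accurate label and accurate figures.

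**What to change.** 1. In Primary Objective 2 and Section 11.0, define the tested quantity as the proportion of treated tumours whose pEGFR/total EGFR ratio is below 20% of the untreated median. Replace 98% and 2% with figures that include estimation of that median from 15 patients, over a stated range of spread. If own-patient inhibition is still claimed, also state a range for its correlation with the untreated ratio.
2. Pre-specify the Group A to Reference Group geometric mean ratio of pEGFR/total EGFR, with a 95% CI from the log scale, as a supporting estimate of average inhibition reported beside the 9-of-18 rule. It does not estimate the responder proportion and should not be presented as if it did.

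The cost is SAP wording, a short simulation and one extra comparison on data already collected, with no new samples or patients. The drawback is that the stated power and false positive rate become less favourable.

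### The PD rule's stated 2% false positive rate and 98% power treat the 80%-reduction cut-off as known, although it is estimated from 15 reference tumours

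*Combined protocol and SAP*

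**What the plan says.** The PD paragraph of Section 11.0 (Primary Objectives and Sample Size) tests a target of 70% of patients "after pulsatile lapatinib treatment assuming a null of 25% patients". A Group A tumour counts as a success if its ratio is at least 80% lower "compared to the median pEGFR/total EGFR ratio for the 15 patients enrolled on the reference arm". Nine or more successes among 18 meet the objective. The paragraph gives 98% power at a true 70% rate and adds that "it yields a false positive rate of 2% for a true 25% rate of such EGFR inhibition".

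The reference group text in the same section says that 15 lapatinib-naïve patients will be "enrolled as a reference group for the PD evaluation to establish the threshold of 80% reduction". It justifies the number by saying that it "yields 90% confidence that the observed median falls between the true" 30th and 70th "percentiles of the pEGFR/total EGFR distribution for untreated patients".

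Nothing in the documents links that precision statement to the 2% and 98%. No adjusted rule, simulation or sensitivity analysis for the cut-off is described.

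**The concern.** A one-sample binomial calculation needs each tumour to be scored against a fixed standard. Here the standard is a sample median. If the 15 reference tumours happen to give a high median, the cut-off is too lenient for all 18 Group A tumours at once; if they give a low one, it is too strict for all of them. This shared error does not average out over Group A, so the number of successes is not binomial with the true rate.

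PD is one of two primary objectives. Section 2.3 reports that at the earlier regimen "lapatinib only inhibited EGFR by about 50" percent, and sets the aim here to "achieve near complete inhibition of pEGFR, defined as 80% reduction of EGFR phosphorylation". The rule therefore has to separate partial from near-complete inhibition, and a cut-off that moves between trials blurs that line. A reader who takes 2% and 98% at face value would have more confidence in a pass or a fail than the design may support.

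**Working it through.** **Inputs from Section 11.0:** success rule of at least 9 of 18; null rate 0.25; target rate 0.70; cut-off = 0.20 × observed median of 15 reference ratios. **Not in the documents, so assumed:** the spread and shape of the log-ratios. The 3-of-8 PK gate is left out, as it is in the plan's own PD figures.

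**1. The plan's figures, cut-off known.**
- P(Bin(18, 0.25) ≥ 9) = 0.0193, stated as 2%.
- P(Bin(18, 0.70) ≥ 9) = 0.9790, stated as 98%.

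**2. The plan's precision statement.** The observed median is the 8th of 15 ordered values, so the true percentile U at which it falls follows Beta(8, 8). P(0.30 < U < 0.70) = 0.900, which reproduces the stated 90%.

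**3. What that does to the cut-off.** For normal log-ratios, z(0.70) = 0.524, so the 30th–70th percentile range puts the cut-off at 0.2 × exp(±0.524 × SD) of the true untreated median.
- SD 0.5: 0.154 to 0.260, a reduction of 74% to 85%.
- SD 1: 0.118 to 0.338, a reduction of 66% to 88%.

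**4. Effect on the rates, normal log-ratios.** Let k = reference log SD / treated log SD. Given U, a true rate p is scored as p* = Φ(z(p) + k·z(U)).

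At the edges of the plan's own interval, with k = 1:
- U = 0.70, p = 0.25: Φ(−0.674 + 0.524) = 0.44, and P(Bin(18, 0.44) ≥ 9) = 0.39.
- U = 0.30, p = 0.70: Φ(0.524 − 0.524) = 0.50, and P(Bin(18, 0.50) ≥ 9) = 0.59.

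Averaging P(Bin(18, p*) ≥ 9) over Beta(8, 8):

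| k | False positive rate | Power |
|---|---|---|
| 0 (known cut-off) | 1.9% | 97.9% |
| 0.25 | 2.3% | 97.5% |
| 0.5 | 3.5% | 96.3% |
| 1 | 8.1% | 91.5% |
| 2 | 19.4% | 80.1% |

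Simulation at k = 1 gives 8.1% and 91.5%. These rates depend on the ratio of the SDs, not on their absolute size.

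**5. Effect if treated tumours are a mixture.** Assume responders with median ratio 3–10% of reference and non-responders with 50–100%, each class with the reference log SD s. With c the log cut-off, p* = w·Φ((c − μ_R)/s) + (1 − w)·Φ((c − μ_N)/s), where w is set so that the true rate at the true cut-off is 25% or 70%. Averaging as in step 4:

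| Within-class log SD | False positive rate | Power |
|---|---|---|
| 0.3 | 1.9–2.0% | 97.7–97.9% |
| 0.5 | 1.9–2.7% | 96.4–98.0% |
| 0.75 | 2.2–4.9% | 94.1–97.9% |
| 1 | 3.0–6.6% | 92.6–97.4% |

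**6. Partial inhibition.** Take the earlier regimen's roughly 50% as a median effect (an assumption), with equal normal log SDs. The chance of passing, known versus estimated cut-off, is 0.2% versus 2.5% at SD 1, and 3.2% versus 10.5% at SD 1.5. With no drug effect at all and an estimated cut-off, it is about 0.02% at SD 1 and 1.0% at SD 1.5.

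**The case against.** **The true rate could mean the rate relative to the observed reference median.** The binomial figures would then be exact. The PD paragraph does call the threshold putative, but this reading fits poorly: the opening of Section 11.0 poses a question about patients with this disease, and the reference group text treats the median as an estimate with true percentiles behind it.

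**The imprecision is disclosed.** It is, and it is used to justify the 15 patients. What is missing is the step from there to the error rates.

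**The size is unknown and may be small.** This stands. The rates barely move if treated tumours vary much more than reference tumours, or if they separate clearly into responders and non-responders. In some mixture cases at log SD 0.3 to 0.5 there is no loss, or even a marginal gain. If treatment adds its own independent variation to the untreated spread, k cannot exceed 1; an added SD equal to the reference SD gives 5.1%/94.6%.

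**Stronger readings that the documents do not support.** A reader might infer that the arithmetic is wrong; it is right for a known cut-off. A reader might take 8% and 92%, or 19% and 80%, as the true rates; the first pair needs normal log-ratios with equal SDs, and the second needs treatment to halve the spread. Nor does the rule readily pass an inactive drug, as the no-effect figures show.

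**Conclusion.** The point stands as an omitted condition. The 2% and 98% hold for a known cut-off, which this design does not have, and the plan's own precision statement is not carried into them. How far the real rates depart cannot be settled from the documents. Under normal log-ratios with treated tumours at least as variable as reference tumours, they could be as unfavourable as about 8% and 92%. Under greater treated variability or a clear split into responders and non-responders, they lie closer to 2% and 98%. The omission itself is certain; the magnitudes are conditional on these assumptions. It should be fixed because it concerns the stated performance of a primary decision rule and the correction is cheap. It gives no reason to change the rule or the sample size.

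**What to change.** Keep the 9-of-18 rule. In Section 11.0, replace the last sentence of the PD paragraph with text such as:

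> For a known threshold, this rule has 98% power at a true 70% rate and a 2% false positive rate at a true 25% rate. Allowing for sampling error in the reference median (n = 15), these could be as unfavourable as about 92% and 8% if log-ratios are normally distributed with equal SDs in the two groups. They would be closer to 98% and 2% if treated tumours are more variable than reference tumours or separate clearly into responders and non-responders. Spread and shape are assumptions, because no estimates are available in this protocol.

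In the analysis, report the Group A proportion with an interval that resamples both groups. A simpler option, since resampling a median of 15 is coarse, is to recompute the proportion with the cut-off set from each confidence limit of the reference median. The 4th and 12th of the 15 ordered values give 1 − 2·P(Bin(15, 0.5) ≤ 3) = 1 − 2 × 576/32768 = 96.5% coverage.

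The cost is a few sentences and a few lines of code, with no extra patients. The downside is that the stated figures become slightly less favourable and depend on named assumptions.

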## **5.0 TOXICITY**

### **5.1 Toxicity Management and Dose Delay/Modification for Lapatinib**

Dose delays and dose modification requirements for clinically significant adverse events or abnormal laboratory values assessed as unrelated to disease progression, intercurrent illness, or concomitant medications are defined in the following sections. Toxicities must have an attribution of possible, probable, or definite to lapatinib (see Section [9.2.2](#)). Adverse events (AEs) should be treated with the appropriate maximum supportive care and should be clearly documented on the case report form.

Group A patients—pre-surgical treatment: Lapatinib is not dose-reduced for toxicities in the pre-surgical dosing period; if treatment is delayed for toxicity such that the patient cannot receive the four lapatinib doses according to the pre-surgical dosing schedule, or if

lapatinib is discontinued, the patient will be replaced in the cohort but may continue with post-surgical treatment provided toxicity from pre-surgical dosing resolves within protocol parameters.

All adverse events will be monitored and collected throughout the trial and documented based on CTCAE version 5.0. If there are three or more delays of scheduled surgery due to lapatinib-related serious adverse events (SAE) among the initial 8 patients; or if there are any surgical complications and delayed wound healing SAEs grade  $\geq 3$  considered lapatinib-related among the first three patients, ABTC investigators will consult with CTEP investigators and the pharmaceutical sponsor about such events. See Section [9.3](#) for SAE information.

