### 5.2.3 Lapatinib dose modification for non-cardiac AEs

Table 5.2.3:

Adverse Events	Grade	Action
Pneumonitis, Pulmonary fibrosis, Adult Respiratory Distress Syndrome (ARDS), Pulmonary edema (non-cardiogenic)	Grade 1 to 4	Patients who develop symptoms or signs suggestive of pulmonary infiltrates or pneumonitis, should have lapatinib interrupted while a thorough evaluation is performed. If pneumonitis is confirmed, permanently discontinue lapatinib. If other parenchymal abnormalities are confirmed and the relationship to lapatinib cannot be excluded, lapatinib must be permanently discontinued.
Rash	Grade 1	No dose modifications. See “supportive care for rash.”

Adverse Events	Grade	Action
	Grade 2	If toxicity is unacceptable to patient or medically concerning, hold lapatinib until recovery to $\leq$ Grade 1 for up to 14 days. Restart at the same dose.  If dose has previously been held for grade 2 toxicity and grade 2 symptoms recur, OR if the patient finds the symptoms unacceptable, hold dose until recovery to $\leq$ Grade 1. See “ supportive care for rash. ” Resume at one dose reduction..
	Grade 3	Hold lapatinib until recovery to $<$ Grade 1 for up to 14 days. See “ supportive care for rash. ” Resume at one dose reduction.
	Grade 4 rash or toxic epidermal necrolysis (e.g., Stevens-Johnson Syndrome, etc.)	Permanently discontinue lapatinib. See “ supportive care for rash. ”
Diarrhea	Grade 1	Continue lapatinib, but start loperamide (initial dose 4 mg followed by 2 mg every 4 hours or after every unformed stool). It is suggested to continue loperamide until the subject is free from diarrhea for 12 hours. See “ supportive care for diarrhea. ”
	Grade 2 to 4	Hold lapatinib until grade 1 or lower (up to 14 days). Start loperamide as above, and other measure. See “ supportive care for diarrhea. ” Resume at one dose reduction.
Abnormal liver function tests (ALT, bilirubin)	Grade 1 or 2 abnormal ALT / bilirubin	Lapatinib must be discontinued permanently for patients with: 1. BOTH bilirubin and ALT abnormalities being of Grade 2 OR 2. EITHER bilirubin OR ALT abnormality is Grade 2 and accompanied by signs or symptoms which, in the opinion of the treating physician, are related to liver injury caused by lapatinib. (Such signs and symptoms may include abdominal pain, fever, jaundice, rash, eosinophilia or a performance status (PS) drop of $\geq 1$ point from baseline.)

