## 9.3 Serious Adverse Events and Expedited Adverse Event Reporting

### 9.3.1 Definition – Serious Adverse Event (SAE)

An adverse event is considered serious if it results in ANY of the following outcomes:

- 1) Death
- 2) A life-threatening adverse event

- 3) An adverse event that results in inpatient hospitalization or prolongation of existing hospitalization for  $\geq 24$  hours
- 4) A persistent or significant incapacity or substantial disruption of the ability to conduct normal life functions
- 5) A congenital anomaly/birth defect
- 6) Important Medical Events (IME) that may not result in death, be life threatening, or require hospitalization may be considered serious when, based upon medical judgment, they may jeopardize the patient or subject and may require medical or surgical intervention to prevent one of the outcomes listed in this definition.

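### The surgery-delay limb of the early safety trigger counts only delays due to lapatinib-related SAEs, so operations postponed by non-serious lapatinib toxicity generally go uncounted

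*Combined protocol and SAP*

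**What the plan says.** The rule appears twice, in nearly the same words. Section 11.0 (initial safety monitoring) has "If there are three or more delays of scheduled surgery due to lapatinib-related Serious Adverse Events among the initial 8 patients", and Section 5.1 has "If there are three or more delays of scheduled surgery due to lapatinib-related serious adverse events (SAE) among the initial 8 patients". The restriction to SAEs is therefore not a slip in one place.

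A second limb follows in the same sentence: "if there are any surgical complications and delayed wound healing SAEs grade" 3 or higher, considered lapatinib-related, among the first three patients. If either limb is met, "ABTC investigators will consult with CTEP investigators and the pharmaceutical sponsor about such events". No pause or stop is attached. Separately, "An internal safety monitoring evaluation will be conducted after the first three patients complete their first follow-up visit after surgery".

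Section 9.3.1 defines an SAE by outcome: death, threat to life, "An adverse event that results in inpatient hospitalization or prolongation of existing hospitalization for" 24 hours or more, incapacity, birth defect, or an important medical event by medical judgment. Postponement of an operation is not on the list.

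For Group A before surgery, Section 5.1 has its own provision: "if treatment is delayed for toxicity such that the patient cannot receive the four lapatinib doses" on schedule, or if lapatinib is discontinued, the patient is replaced. That provision has no seriousness condition. Section 4.1 likewise replaces patients who receive fewer than four doses. Neither section says whether a replaced patient still belongs to the initial 8 for the safety count.

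**The concern.** The limb counts delayed operations, and its presence shows that the authors thought lapatinib toxicity could delay surgery. For a patient with recurrent high-grade glioma the harm is the postponed resection, whatever regulatory label the causing event carries. The SAE filter sorts events on a different scale.

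The documents give some reason to think that part of the relevant toxicity would be non-serious. Section 9.2.1 lists diarrhea among events seen in more than 20% of patients. Section 2.2 reports that most of the common adverse events were grade 1 or 2. Section 4.3 makes dosing outpatient. Section 2.2 also says that no experience with the pulsatile regimen around surgery has been identified, so an early signal has particular value.

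As written, three or more of the first eight patients could have surgery postponed for lapatinib toxicity without the consultation being called. Nothing else in the plan supplies a delay criterion. The second limb concerns surgical and wound-healing SAEs in three patients, and the internal evaluation is tied to the first three patients and names no delay threshold. Patients 4 to 8 are covered for delay only by the SAE-filtered count.

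**Working it through.** **Inputs from the documents.** Threshold 3, denominator 8, qualifying event a delay due to a lapatinib-related SAE (Sections 5.1 and 11.0). No operating characteristic is stated for the trigger, and no delay or SAE rate is given. All rates below are assumptions.

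**Formula.** With a per-patient probability p of a counted delay and independent patients,

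P(at least 3 of 8) = 1 − (1−p)^8 − 8p(1−p)^7 − 28p²(1−p)^6.

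**Check against the plan's own figure.** The PK futility rule in Section 11.0 uses the same cut (no more than 2 of 8). At p = 0.25, P(at most 2) = 0.1001 + 0.2670 + 0.3115 = 0.6785, against 68% stated. At p = 0.70 it is 0.0113, against 1.1% stated. Both reproduce.

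**The delay limb.** Let q be the share of patients whose surgery is delayed by lapatinib toxicity of any seriousness, and s the share of those delays due to an SAE. The wider count uses p = q; the current rule uses p = q × s. For example, q = 20% and s = 25% give p = 5%, and 1 − (0.6634 + 0.2793 + 0.0515) = 0.0058.

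| q (assumed) | all delays count | current rule, s = 25% | s = 50% | s = 75% |
|---|---|---|---|---|
| 10% | 3.8% | 0.1% | 0.6% | 1.8% |
| 20% | 20.3% | 0.6% | 3.8% | 10.5% |
| 30% | 44.8% | 1.8% | 10.5% | 26.0% |
| 40% | 68.5% | 3.8% | 20.3% | 44.8% |

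**Extra consultations when delays are rare.** If only 5% of patients are delayed by lapatinib toxicity of any kind, the wider count fires in 0.6% of trials; at 10% it fires in 3.8%.

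**The second limb.** With w the rate of qualifying surgical or wound-healing SAEs, P(at least 1 of 3) = 1 − (1−w)^3: 14.3% at w = 5% and 27.1% at w = 10%. It does not depend on how delays are counted.

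**The case against.** The strongest reply has four parts.

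*Interrupted dosing is not a postponed operation.* The provisions for pre-surgical toxicity in Sections 4.1 and 5.1 deal with missed doses and replacement. They do not say that surgery then waits. Under Section 3.2 the operation is clinically indicated by the care providers, and Section 4.1 no longer requires tissue from patients with fewer than four doses. The diarrhea row of Table 5.2.3 ("Hold lapatinib until grade 1 or lower (up to 14 days") is weak support too, since it continues with a dose reduction that Section 5.1 rules out before surgery. This stands. A reader might infer that the protocol expects toxicity to interrupt the pulse and so delay surgery, but the text is conditional and gives no frequency. The point rests only on the limb's own premise that lapatinib toxicity can delay surgery.

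*The trigger is not inert.* A reader might infer that it can hardly fire. The documents do not show that. The delay limb fires in 20.3% of trials if SAE-caused delays occur in 20% of patients, 44.8% at 30% and 85.5% at 50%, and a single qualifying event meets the second limb.

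*The SAE definition is elastic.* An event that postpones a craniotomy might be classed as an important medical event. This also stands, but the count then depends on each investigator's classification.

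*Other monitoring exists.* All adverse events are collected, Group A patients are assessed on the day of surgery (Section 9.1), and nothing forbids earlier consultation. Reserving formal escalation for serious events is a defensible choice. This lowers the priority of the point but does not supply a delay criterion for patients 4 to 8.

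**Conclusion.** The point holds in a limited form. In both places where it appears, the delay limb omits operations postponed by non-serious lapatinib toxicity unless the event is judged an important medical event, and no other rule counts them. The loss of sensitivity could be large or small. With 20% to 40% of patients delayed, the chance of reaching 3 of 8 falls from 20.3%–68.5% to 0.6%–3.8% if a quarter of the delays are serious, to 3.8%–20.3% if half are, and to 10.5%–44.8% if three quarters are. If nearly all such delays were serious, little would be lost. These figures rest on assumed rates and on independence between patients; the documents fix none of the rates.

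Because the trigger leads only to consultation, this is an inexpensive improvement of modest priority. The primary PK and PD analyses are not affected.

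**What to change.** In Sections 5.1 and 11.0, make the delay limb count delays of scheduled surgery *due to any adverse event at least possibly related to lapatinib, serious or not*. Section 5.1 already uses an attribution of possible, probable or definite for dose changes, and Section 9.2.3 already has investigators record attribution, so no new attribution scale is needed. Keep 3 of 8, the consultation and the second limb as they are.

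Add one sentence stating that patients replaced for pre-surgical toxicity remain in the initial 8 for this count. Without it, a patient whose toxicity both broke the four-dose schedule and delayed surgery could drop out of the denominator.

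The cost is one phrase in two sections plus that sentence. The downside is that the consultation, which is not a stopping rule, may be called somewhat more often.
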